5.3 ASSIGNMENT & BLINDING

Subjects meeting the Inclusion and Exclusion criteria will be enrolled and randomized into either Treatment or Control groups. The randomization algorithm will be blocked to account for site bias and to ensure counterbalance across sites. As this is an open label study, there will be no consideration for blinding.

6. STUDY ENDPOINTS

6.1 PRIMARY ENDPOINTS

6.1.1 Primary Safety/ Tolerability Endpoints:

- Safety/Tolerability will be assessed by the non-inferiority of incidence of serious adverse events (SAEs), unanticipated SAES (USAEs), device-related SAEs (DSAEs) and Unanticipated Device Related SAEs (UDAEs) that are associated with the TENS therapy throughout the therapy/treatment period versus historical control.
- Safety variables will be tabulated and presented for all subjects including enrolled, but discontinued, subjects. Number of subjects undergoing TENS and any reasons for discontinuation of study treatment will be tabulated.
- Safety variables will be collected over a 6 month duration.

6.1.2 Primary Effectiveness Endpoint:

The primary efficacy endpoint is the percent reduction in appetite suppression as measured by percent change in appetite scores at the end of 3 months of the Therapy period compared to Baseline between Treatment and Control.

A co-primary endpoint will be total body weight loss (%TBWL), measured as $\text{End Weight} - \text{Initial Weight}$ divided by Initial Weight, multiplied by 100, at the end of 3 months of the Therapy period compared to Baseline between Treatment and Control.

6.1.3 Secondary Effectiveness Endpoints:

- Number of subjects reporting >5% total body weight loss at the end of 3 months of the Therapy period as compared to Baseline between Treatment and Control
- Blood pressure, blood lipids, and HbA1c at the end of 3 months of the Therapy Period as compared to Baseline between Treatment and Control groups.
- % changes in BMI at the end of 3 months of the Therapy Period compared to Baseline between Treatment and Control groups.

6.1.4 Ancillary Endpoints:

- Cross validation between smartphone app hunger scales and paper VAS diaries collected at the same times.

Changes between the following values:

- Ease of use/prevalence of use errors associated with the patch unit and dietary application during initial training.
- Subject preference scores at the end of Therapy Period compared to Baseline between Treatment and Control groups.

Protocol #: CD-005; Version #: 4.0

Original Date: May 8, 2018 Revision Date: May 3, 2019

-Confidential-

6.2 ENDPOINT DEFINITIONS & RECORDING METHODS

Endpoint data in hunger, appetite, and dietary compliance are obtained from subject reported assessments (Appendix 4, 5). That is, the measurement of success is based on the subject's report of the parameter using validated tools where available.

Primary source data will be paper based, with each subject receiving diary worksheets to record responses. Treatment subjects will also be assigned an Android Smart Phone onto which has been loaded a copy of custom dietary application (Appendix 5). Subjects will be trained on the use of these tools and assessed for accurate use prior to taking them home. To ensure data privacy, the network interface card (i.e. SIM card) for the phone will be removed such that data can only be downloaded *via* a direct USB link.

7. STUDY POPULATION

7.1 INCLUSION CRITERIA

- 7.1.1 Subject is between 18 – 65 years of age inclusive.
- 7.1.2 Subject has a BMI of 25-35 kg/ m² inclusive.
- 7.1.3 Subject has signed the informed consent form and is able to comply with study protocol and adhere to study visit schedule.
- 7.1.4 Subject is able to wear and use a wearable, patch TENS system.
- 7.1.5 Subject is able to use a touch screen hand held smart phone.
- 7.1.6 Subject is fluent in English and can complete questionnaires.
- 7.1.7 Females of childbearing potential (FOCBP) must have a negative urine pregnancy test at screening or enrollment visit, prior to placement of ELIRA device.
- 7.1.8 Subject is male or non-pregnant, non-lactating female, who agrees to use effective contraceptive methods throughout the length of the trial based on PI approval.

7.2 EXCLUSION CRITERIA

- 7.2.1 Subject has any known gastrointestinal disorder that in the opinion of the PI precludes enrollment into the trial.
- 7.2.2 Subject has had a prior bariatric procedure or any previous procedure on the stomach.
- 7.2.3 Subject has any significant multisystem disease in the opinion of the PI.
- 7.2.4 Subject has > 6.5 HbA1c.
- 7.2.5 Subject has significant cardiac arrhythmia, ectopy, or significant cardiovascular disease.
- 7.2.6 Subject has an existing implanted electrical stimulator (e.g., pacemaker, AICD).
- 7.2.7 Subject is a female of child-bearing potential who is pregnant or intends to become pregnant during the trial period.
- 7.2.8 Subject has current and/or a history of cancer within the past 5 years (not including basal cell carcinoma or cervical carcinoma in situ).
- 7.2.9 Subject has had a weight change of \pm 5% of his/her Total Body Weight in the 3 months prior to screening.
- 7.2.10 Subject has a moderate / severe psychiatric disorder.
- 7.2.11 Subject has a diagnosed neurological disease.
- 7.2.12 Subject has a diagnosed eating disorder.
- 7.2.13 Subject has a skin disorder affecting the thoracic dermatomes.
- 7.2.14 Subject has active or /has ever had shingles in the abdominal area.
- 7.2.15 Subject has abdominal surgery or other scars which may interfere with TENS stimulation in the opinion of the PI.
- 7.2.16 Subject is currently enrolled in other potentially confounding research.
- 7.2.17 Subject has known allergic reaction to materials in the TENS electrodes and/or is otherwise unable to tolerate stimulation with the wearable TENS system. This includes known allergies to latex, nickel and/or hydrogels.

- 7.2.18** Subject has a history of sensitive skin, including eczema wheel-and-flare or other skin irritation, per PI discretion.
- 7.2.19** Subject is actively participating or unwilling to discontinue participation in another weight loss program. Subjects may not enroll in paid or unpaid programs that involve in-person or online apps or coaching, beginning new fitness regimens or utilizing meal planning or paid nutritional coaching during the course of the ELIRA study
- 7.2.20** Subject is taking weight loss control medications including but not limited to OTC medications, Metformin, and Belviq. (See Appendix 8)
- 7.2.21** Subject is planning any major medical treatments or surgeries that could cause weight loss.
- 7.2.22** Subject is unable to take anti-nausea medications planned for the study.
- 7.2.23** Inability to walk at least 0.8 kilometers per day (10 minutes of continuous walking).
- 7.2.24** Current smoker or user of nicotine product or smoking cessation within 1 year of the screening date.
- 7.2.25** History of treatment for or current abuse of drug or alcohol.
- 7.2.26** A score of ≥ 10 on the Patient Health Questionnaire 9 (PHQ-9), demonstrating moderate depression.
- 7.2.27** Any subject that the investigator considers inappropriate for the study for medical reasons.
- 7.2.28** Subject has a history of moderate/severe migraines or other severe headache disorders requiring the treatment of Topiramate.
- 7.2.29** Subject is on drug therapy which may alter antral motility or appetite, per PI discretion. (Appendix 8).

7.3 SELECTION AND ENROLLMENT OF SUBJECTS

Prospective study subjects will be screened for study eligibility. A subject is considered enrolled after:

1. Written Informed Consent is obtained.
2. Meeting all inclusion and exclusion criteria and randomized into the study.
3. This study will utilize unique subject numbers for the purpose of trial data collection. Subjects signing an Informed Consent but not meeting all criteria will not be considered enrolled in the study, but the signed Informed Consents will be maintained by the PI for seven (7) years.

Following enrollment, subjects should remain in the study until completion of the required Therapy Phase.

A subject's participation may be discontinued for the following reasons:

- Subject Withdrawal: As subject participation in a clinical trial is voluntary, the subject may choose to discontinue participation at any time without penalty or loss of benefits.

- Investigator Termination: The Investigator may terminate the subject's participation without regard to the subject's consent if the Investigator believes termination is medically necessary.
- Lost-to-Follow-up: A subject is lost-to-follow up if he/she does not complete required follow-up, but has not "officially" withdrawn consent. In order to consider a subject lost to follow-up, site personnel should make all reasonable efforts to locate and communicate with the subject. A minimum of three (3) attempts to contact the subject should be recorded in the source documentation including date, time and name of site personnel attempting to make contact.

8. STATISTICAL CONSIDERATIONS AND ANALYSIS PLAN

8.1.1 General Methods

Categorical variables will be summarized by number and percent. Continuous variables will be summarized by total number (N), mean, standard deviation (SD), median, minimum and maximum. Ninety-five percent, 2-sided confidence intervals will be reported, as appropriate.

As this was a randomized trial, the groups are expected to be balanced on demographic and baseline characteristics. No formal testing for this is planned.

Planned analyses and summaries for the primary safety endpoint, co-primary efficacy endpoints, secondary efficacy endpoints and exploratory efficacy endpoints are detailed below.

8.1.2 Analysis Populations

The intent to treat (ITT) analysis population is defined as all subjects who were enrolled.

The modified intent to treat (mITT) analysis population is defined as all subjects who initiated therapy (i.e., initiated their first Treatment Period Visit) and had data through week 12. All safety and effectiveness analyses will be completed on the mITT analysis population.

The per protocol (PP) analysis population is defined as all subjects who met all inclusion/exclusion criteria, completed all visits in the study without any major protocol deviations. All effectiveness analyses will be completed on the PP analysis population.

8.1.3 Safety Analyses

The primary safety endpoint is defined as the proportion of subjects free of TENS-related serious adverse events and adverse device effects through the therapy phase, safety success rate. The success rates will be compared between groups using chi-square test or Fisher's exact test, as appropriate.

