
Study Endpoints
	
Primary Safety/Tolerability Endpoint:
 
Safety/Tolerability will be assessed by the non-inferiority of incidence of serious adverse events (SAEs), unanticipated SAEs(USAEs), device-related SAEs (DSAEs) and Unanticipated Device Related SAEs (UDAEs) that are associated with the TENS therapy throughout the stimulation and the follow-up period versus historical control (compared with other TENS systems).
 
Safety variables will be tabulated and presented for all subjects including enrolled, but discontinued, subjects. Number of subjects undergoing active stimulation and any reasons for discontinuation of study treatment will be tabulated.
 
Safety/Tolerability will be assessed through 6 months of therapy.
 
Primary Effectiveness Endpoint:
 
The primary efficacy endpoint is the percent reduction in appetite suppression as measured by percent change in appetite scores at the end of 3 months of the Therapy period compared to Baseline between Treatment and Control.
 
A co-primary endpoint will be total body weight loss (%TBWL), measured as End Weight – Initial Weight divided by Initial Weight, multiplied by 100, at the end of 3 months of the Therapy period compared to Baseline between Treatment and Control.
 
Secondary Effectiveness Endpoints:
 
Number of subjects reporting >5% total body weight loss at the end of 3 months of the Therapy compared to Baseline between Treatment and Control
 
Blood pressure, blood lipids, and HbA1c at the end of 3 months of the Therapy compared to Baseline between Treatment and Control groups.
 
% changes in BMI at the end of Therapy compared to Baseline between Treatment and Control groups
 
Ancillary Endpoints:
 
Cross validation between smartphone app hunger scales and paper VAS diaries collected at the same times.
 
Changes between the following values:
 
Ease of use/prevalence of use errors associated with the patch unit and dietary application during initial training.
 
Subject preference scores at the end of Therapy compared to Baseline between Treatment and Control groups.

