
Statistical Analysis
	
Statistical Analysis Plan, 2019MAY31
 
ELIRA -2 Trial: Safety and Effectiveness of Transcutaneous Electrical Nerve Stimulation (TENS)-Assisted Weight Loss and/or Appetite Suppression
 
Protocol Number: CD-005, Original Date:2018MAY08, V4.1, Revised Date:2018AUG14
 
Signature Page
 
Author: [name] _____ Date _____
 
Approver: _____ Date _____
 
Approver: _____ Date _____
 
STATISTICAL CONSIDERATIONS AND ANALYSIS PLAN
 
General Methods
 
Categorical variables will be summarized by number and percent. Continuous variables will be summarized by total number (N), mean, standard deviation (SD), median, minimum and maximum. Ninety-five percent, 2-sided confidence intervals will be reported, as appropriate.
 
As this was a randomized trial, the groups are expected to be balanced on demographic and baseline characteristics. No formal testing for this is planned.
 
Planned analyses and summaries for the primary safety endpoint, co-primary efficacy endpoints, secondary efficacy endpoints and exploratory efficacy endpoints are detailed below.
 
Analysis Populations
 
The intent to treat (ITT) analysis population is defined as all subjects who were enrolled.
 
The modified intent to treat (mITT) analysis population is defined as all subjects who initiated therapy (i.e., initiated their first Treatment Period Visit) and had data through week 12. All safety and effectiveness analyses will be completed on the mITT analysis population.
 
The per protocol (PP) analysis population is defined as all subjects who met all inclusion/exclusion criteria, completed all visits in the study without any major protocol deviations. All effectiveness analyses will be completed on the PP analysis population.

------------------------------------	---

Safety Analyses

The primary safety endpoint is defined as the proportion of subjects free of TENS-related serious adverse events and adverse device effects through the therapy phase, safety success rate. The success rates will be compared between groups using chi-square test or Fisher's exact test, as appropriate.

Efficacy Analyses***Co-Primary Efficacy Analyses***

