4. STUDY OBJECTIVES

The objectives of this study are to demonstrate safety and effectiveness of a wearable patch TENS system (Appendix 2) in driving weight loss and appetite suppression when coupled with an integrated weight loss reduction strategy. The study is designed to demonstrate that TENS stimulation sufficient to drive weight loss and appetite suppression is safe and tolerable when compared to standard of care, and that adverse events/adverse device effects are similar to other TENS device use cases.

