5. STUDY DESIGN

[figure not shown]
Randomized, adaptive parallel arm study. Subjects will be initially screened during a screening period (1 week, ± 7 days; Figure 2). During this screening period, prior to study procedures being performed, subjects will sign an informed consent form. Then they will have their weight and blood pressure measured, FOCBP will have a pregnancy test, get blood drawn for analysis (blood lipids, HbA1c), and complete patient preference questionnaires. At the end of the screening/baseline period, eligible subjects will be offered the chance to enroll in the study. After enrolling, subjects will be randomized to treatment or control groups.

The Treatment group will be instructed to follow a healthy diet that they will follow for the duration of the study and will receive training on the use of the paper diaries, electronic scale, smartphone app and the Elira wearable patch system. All treatment subjects will be required to stimulate in the office for up to 30minutes to confirm sufficient system training and to acknowledge understanding stimulation settings. A below neck photograph will be taken of the treatment group in requested attire (i.e. biker shorts and sports bra for women, biker shorts for men). Following this, subjects will enter the Therapy Period, for a ~24-week duration. Treatment subjects may be contacted by PI or clinical coordinator to address any questions related to device functionality or compliance. Device usage will be monitored throughout therapy phase to ensure proper functionality and subject safety.

The Control group will be instructed to follow a healthy diet that they will follow for the duration of the study and will receive training on the use of the weekly paper diary and electronic scale. The Control group will not receive the electronic smartphone app or the Elira wearable patch system/components.

At the end of the 3 months of the Therapy Period, all subjects will be assessed for weight loss, blood pressure, blood lipids, HbA1c, and will continue to participate through months 4-6 to confirm the long term safety of the device prior to being terminated from the study. A below neck photograph will also be taken at the 12 week visit.

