9. STUDY PROCEDURES

The study is divided into four phases as defined below (See Appendix 66 for Schedule of Visits):

Study Phase	Definition
Screening Visit	Obtain Informed Consent. Completion of Pre-Study Survey. Determination of Inclusion and Exclusion criteria (including PHQ-9 questionnaire; Appendix 3), Medical History and Physical, Obtain Concomitant Medications, Weight Loss History, Blood Pressure, Height and Weight, Blood Tests (including a lipid panel, HbA1c, and Urine Pregnancy Test for FOCBP. Dispense and Instruct on completion of Weekly Diary.
Randomization / Enrollment Visit	
Confirm Inclusion/Exclusion criteria has been met, Weight, blood pressure, and AEs/Concomitant Medications assessed. Completion of baseline TFEQ-R18V2 (Appendix 4). Assessment of T6/T7 Dermatomes, UPT for FOCBP (if not done at screening). Completion of pre-enrollment photographs.
 
Randomization of subject. For both groups (control and treatment) train and dispense paper diaries and electronic scale, encourage low-calorie diet for duration of study, provide Diet Resources sheet (Appendix 18.11)
 
In Addition, For Treatment Group only, training) and assessment of use of smart phone app and Elira wearable patch system (Appendix 2); Initiation of therapy and dose adjustment. Provide TENS Clean-Cote Skin Wipes and/or Alcohol Prep Pads and Cetaphil Moisturizing Lotion with instructions on use, following a healthy low-calorie diet, as needed, dispense smart phone app and Elira wearable patch system. ELIRA Device training (Treatment Group). Paper VAS sheets

Therapy Period	
For Control and Treatment Groups: Confirm Inclusion/Exclusion criteria continues to be met, collect blood pressure, AEs, and review Adverse Device Events, paper diary (dispense additional diaries), weight, blood pressure, assess for AE's/concomitant medications, completion of hunger and Completion of TFEQ-R18V2, encourage continuation of low-calorie diet at each scheduled visit. Blood Tests taken at 12 weeks for lipids and HbA1c. Photographs will be taken at 12 weeks .
 
In Addition, For Treatment Group only: assess for Adverse Device Effects at each visit. Collect Elira wearable patch system and smart phone and download data, assess subjects use of electronic diary, completion paper sheets and stimulation sessions at each visit. Dispense smart phone app and Elira wearable patch system at each visit.

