18.6 APPENDIX 6: SCHEDULE OF EVENTS

APPENDIX 6: SCHEDULE OF VISITS

STUDY PERIOD	SCREENING	ENROLLMENT	THERAPY/CONTROL						END OF STUDY ⁷
	VISIT 0	VISIT 1	VISIT 2	VISIT 3	VISIT 4	VISIT 5	VISIT 6	VISIT 7	VISIT 8
WEEK #	WEEK -1	WEEK 0	WEEK 1	WEEK 4	WEEK 8	WEEK 12	WEEK 16	WEEK 20	WEEK 24
VISIT WINDOW ¹	±7 DAYS	±7 DAYS	±7 DAYS	±7 DAYS	+/- 7 DAYS	+/- 7 DAYS	+/- 7 DAYS	±7 DAYS	±7 DAYS
Informed Consent	X								
Inclusion/Exclusion Criteria	X	X	X	X	X	X	X	X	X
Medical History	X								
Diet History	X								
Physical Exam	X								X
T6/T7 dermatome assessment	X ³	X ³	X ⁴	X ⁴	X ⁴	X ⁴	X ⁴	X ⁴	X ⁴
Blood Pressure	X	X	X	X	X	X	X	X	X
Height	X								
Weight	X	X	X	X	X	X	X	X	X
Laboratory Requisition - Blood Tests ²	X					X			X
Urine Pregnancy Test (FOCBP)	X	X ⁶							X
Administration of PHQ-9	X								X

Protocol #: CD-005; Version #: 4.0

Original Date: May 8, 2018 Revision Date: May 3, 2019

-Confidential-

Administration of TFEQ-R18V2		X	X	X	X	X	X	X	X
Administration of Pre-Study Survey	X								
Administration of Post-Study Survey									X
Provide/Train on Paper Diaries ³	X	X		X	X	X	X	X	
Collect and Review Paper Diaries ³			X	X	X	X	X	X	X
Randomization ⁵		X							
Provide/Train on Electronic Scale		X							
Provide and Train on Electronic Diary Application ⁴		X	X	X	X	X	X	X	
Collect and Review Electronic Diary ⁴			X	X	X	X	X	X	X
Provide and Train on TENS Unit and Patches ⁴		X	X	X	X	X	X	X	
Collect and Examine TENS Unit and Patches ⁴			X	X	X	X	X	X	X
Training on Electrode Placement ⁴		X	X	X	X	X	X	X	
Adjust TENS Unit, if applicable ⁴		X	X	X	X	X	X	X	
Provide/instruct (as needed) on TENS Clean-Cote Skin Wipes an/or Alcohol Prep Pads ⁴		X	X	X	X	X	X	X	
Provide/Instruct (as needed) on Cetaphil Lotion ⁴		X	X	X	X	X	X	X	
Concomitant Medication Review ³	X	X	X	X	X	X	X	X	X
Assessment of Adverse Events ³	X	X	X	X	X	X	X	X	X
Assessment of Adverse Device Effects ⁴		X	X	X	X	X	X	X	X
Schedule next visit	X	X	X	X	X	X	X	X	
Photographs taken		X				X			X
Study Exit									X

1 – all visits are ± 1 week

2 – Blood tests include HbA1c, lipid panel,

3 – to be completed for control and treatment group

4 – to be completed for treatment group only

5 – randomization into control or treatment group

[figure not shown]
6- Either Screening or Randomization Visit, Not Needed at Both.

Protocol #: CD-005; Version #: 4.0

Original Date: May 8, 2018 Revision Date: May 3, 2019

-Confidential-

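### Primary safety is framed as non-inferiority to historical TENS, but the planned test compares device-related events with a control arm that has no device, and the safety population is defined two ways

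*Combined protocol and SAP*

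**What the plan says.** **Hypothesis.** Section 6.1.1 states: "Safety/Tolerability will be assessed by the non-inferiority of incidence of serious adverse events (SAEs", and goes on to list unanticipated, device-related and unanticipated device-related serious events. The comparator is historical. The Study Endpoints row of the Protocol Summary identifies it: "versus historical control (compared with other TENS systems". Section 4 gives the aim as showing that stimulation is "safe and tolerable when compared to standard of care, and that adverse events/adverse device effects are similar to other TENS device use cases".

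**Analysis.** Section 8.1.3, and the same text in the Statistical Analysis row of the Protocol Summary, defines the endpoint as the "proportion of subjects free of TENS-related serious adverse events and adverse device effects through the therapy phase". The method is: "The success rates will be compared between groups using chi-square test or Fisher's exact test, as appropriate".

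**Exposure and ascertainment.** Section 5 says: "The Control group will not receive the electronic smartphone app or the Elira wearable patch system/components". The Therapy Period row of section 9 says: "In Addition, For Treatment Group only: assess for Adverse Device Effects at each visit". In Appendix 6 the row for adverse device effects carries the footnote "4 – to be completed for treatment group only".

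**Population.** Section 8.1.2 puts all safety analyses on the mITT set, which requires therapy to have started and data through week 12. Section 8.4 puts safety on all enrolled subjects, and defines mITT without the week-12 condition. Section 6.1.1 tabulates safety for discontinued subjects as well, and section 8.3 keeps partial data from dropouts.

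**The concern.** The endpoint section and the analysis section ask different questions. The first asks whether this device has no more serious events than other TENS systems, by some margin. The second asks whether two randomised arms differ in events attributed to TENS, when only one arm has TENS.

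The second question has a known answer on the control side, so the test carries no information about the first. A significant difference would not show that the device is worse than other TENS systems. A non-significant one would not show that it is non-inferior to them. The text gives no historical rate, no margin and no one-sample test, so the similarity aim in section 4 has no analysis behind it.

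The population conflict matters separately. Under section 8.1.2 a subject who leaves before week 12 drops out of the primary safety rate. The Visit Schedule says severe skin irritation may end a subject's participation, so some of those excluded could be the subjects with device harm.

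**Working it through.** The plan states no safety rate, margin, alpha or power, so there is no figure to reproduce. The check is a comparison of the texts followed by illustrations.

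**1. Texts side by side**

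| Element | Sections 6.1.1 and 4, Study Endpoints | Section 8.1.3, Statistical Analysis row |
|---|---|---|
| Comparator | Historical TENS | Randomised control without a device |
| Hypothesis | Non-inferiority | Difference |
| Events | Serious events | TENS-related serious events and adverse device effects |

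Whether the last cell is limited to serious device effects is unclear from the grammar. Read literally it is not. That matters because section 9.12.1 describes mild tingling or burning as a typical response, and section 10.1.2 lists paresthesia and burning sensation as adverse events, although at an anticipated low frequency.

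**2. Inputs**
- 80 per arm (section 8.2).
- 56 per arm = 80 × (1 − 0.30), using the 30% dropout in section 8.2. This assumes all dropout falls before week 12, which the plan does not say.
- 150 per arm = 300 / 2, from the maximum enrolment in the Protocol Summary, assuming equal arms.
- Control events: 0, by construction.
- Assumed: two-sided alpha 0.05; historical rates of 1% to 20%.

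**3. What the planned test detects.** With x treated events, none in controls and n per arm, the two-sided Fisher p-value is 2 × C(n, x) / C(2n, x).
- n = 80, x = 5: 2 × (80·79·78·77·76) / (160·159·158·157·156) = 0.059.
- n = 80, x = 6: multiply by 75/155, giving 0.028.

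As n grows, the p-value rises towards 2 × 0.5^x, which is 0.0625 for five events and 0.031 for six. The threshold is therefore six events at every size from 25 to 150 per arm, whatever rate that represents:

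| n per arm | 5 events as a rate | Fisher p | Exact 95% upper limit |
|---|---|---|---|
| 56 | 8.9% | 0.057 | 19.6% |
| 80 | 6.3% | 0.059 | 14.0% |
| 150 | 3.3% | 0.060 | 7.6% |

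The limits are Clopper-Pearson: the 0.975 quantile of Beta(x + 1, n − x).

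**4. A device that exactly matches historical TENS.** The probability of a significant Fisher test is P(X ≥ 6) with X ~ Binomial(n, p):

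| n per arm | p = 1% | 2% | 5% | 10% | 20% |
|---|---|---|---|---|---|
| 56 | <0.1% | 0.1% | 6.0% | 49% | 98% |
| 80 | <0.1% | 0.5% | 21% | 82% | 99.9% |
| 150 | 0.4% | 8.2% | 77% | 99.8% | >99.9% |

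**5. Effect of the population.** With no events at all, the exact upper limit is 1 − 0.025^(1/n): 4.5% for 80 treated and 6.4% for 56. This ignores the larger problem that the 24 missing subjects (80 − 56) need not be a random subset.

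**The case against.** Several points can fairly be made for the plan.

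- **Rare events.** If only serious events count, low rates are the natural case. Table 4 shows that a matching device would then seldom be flagged at 80 per arm. This stands, but the other failure remains: a non-significant test is still not evidence of non-inferiority.
- **Choice of test.** The plan also allows chi-square. Uncorrected, that is significant from four events (p = 0.043 at 80 per arm). With six events the expected count per arm is 6/2 = 3, so Fisher is the usual choice, but the threshold of six is specific to Fisher.
- **Standard of care.** Section 4 also names this comparison, which could justify a between-arm test. It would justify one on all-cause events, not on events that only one arm can have.
- **Control ascertainment.** Section 9 lists a review of adverse device events for both groups. A control has no device to cause one, and the same table and Appendix 6 assign the assessment of device effects to treated subjects.
- **Consequences.** Study success in section 8.1.4 rests on efficacy alone, no safety pass rule is set, and events are tabulated for everyone. Harm is therefore not hidden. This limits the damage, but a primary endpoint still has no analysis that answers it.

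**Conclusion.** The concern holds and should be fixed before analysis. Two contradictions stand on the text alone and need no assumed rate: the hypothesis against the test, and mITT against all enrolled subjects. A third point, whether non-serious device effects count, needs clarifying.

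The numerical size depends on Fisher's test, two-sided 0.05, equal arms and the assumed historical rate. At 80 per arm a device equal to historical TENS is called different in under 1% of trials at a rate of 1–2% and in 21% to 99.9% at 5–20%. Five events pass as non-significant while remaining compatible with a true rate of up to 14.0%. The results at 56 per arm also assume that all of the 30% dropout occurs before week 12.

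**What to change.** - **Section 8.1.3 and the Statistical Analysis row:** replace the between-arm test with the treated-arm event proportion and its Clopper-Pearson 95% interval.
- **Section 6.1.1 and the Study Endpoints row:** keep non-inferiority only if a sourced historical TENS rate and margin are fixed before the data are seen. Otherwise drop the claim and report descriptively.
- **Events:** report device-related serious events separately from non-serious device effects, and state which of them make up the primary rate.
- **Standard of care:** show all-cause serious events by arm, descriptively.
- **Population:** remove safety from the mITT sentence in section 8.1.2 and its copy in the Protocol Summary. Use all enrolled subjects for tabulations and all treated subjects as the denominator of the device-event proportion. The treated set is not defined at present and must be added. The two mITT definitions should be reconciled at the same time.

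The cost is wording, plus a sourced rate if the claim is kept. No procedures change. The drawback is power. Take as the rule that the upper 97.5% exact limit must fall below the historical rate plus the margin, with the true rate equal to a historical rate of 1–10%. Power is then 18–52% at 80 treated and 0–32% at 56 with a 5-point margin, and 59–99% and 51–89% with a 10-point margin. The safety claim may therefore have to be descriptive.
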